11.4.5 Exploratory Analysis

This study provides the opportunity to explore important research questions. The quality of evidence from these analyses will be considered inferior to the evidence that results from the analysis of primary and secondary objectives. The following issues will be investigated:

1. The effect of treatment on pain and the relationship between pain and treatment efficacy.
 - a. The relative efficacy of EMM vs. SMM depending the patient's pain status at baseline (interaction between chronic pain and treatment) will be studied. If the relative efficacy does not depend on baseline chronic pain (lack of significant interaction effect), whether pain during the treatment period affects the efficacy of the treatments will be investigated (test for main effect of pain in a model with main effects only). Appropriate logistic regression models using GEE to account for within site correlation will be used. The probabilities for substantial improvement at three and six months will be modeled as functions of treatment, pain status, and their interaction. A significant interaction effect would indicate that the relative efficacy of EMM vs. SMM depends on pain status. If the interaction effect is not statistically significant at level $\alpha=0.05$, a model with main effects of pain and treatment will be fit and the effect of pain will be estimated from this model.
 - b. For patients with chronic pain at baseline, the course of pain during the three months of treatment and during the follow up will be studied. This will be done using an approach similar to a) above and shown by Model 1.
2. A history of any heroin use: whether the history of any heroin use moderates the effect of treatment on the rate of substantial improvement will be studied.
3. The reason for addiction to prescription opioids: how the patient became addicted to prescription opioids will be explored; whether through illicit use unrelated to pain or due to an initial legitimate prescription to pain. Whether this factor moderates the effect of EMM on substantial improvement will be examined.
4. Coexisting psychiatric illness: Whether a history of PTSD or major depressive disorder, both common in this population, moderate the effect of treatment on the rate of substantial improvement will be studied.
5. Craving during treatment and its relationship to treatment outcome.
 - a. Effect of treatment on craving: The weekly craving measures will be studied to assess whether the two treatments affect the course of craving symptoms differently. The following model will be used:

(1)

$$(2) E(Y_{ijt}) = \beta_0 + \beta_1 txt_{ij} + \beta_2 t + \beta_{12} t^* txt_{ij} + \beta_{2t} I_{ij}^s + \beta_{12} I_{ij}^s txt_{ij} ,$$

where Y_{ijt} is mean craving scores, measured by VAS, of j^{th} patient in the i^{th} site at time t , ($t=1$ to 12). Testing the hypothesis is equivalent to testing for significance of \hat{a}_{12} . The presence of a significant interaction of treatment and time would indicate that the decrease of self-reported craving will be faster in the EMM groups than in the SMM group. If the interaction term is not significant, the significance of \hat{a}_1 from a model with main effects only will be tested. The presence of a significant treatment effect would indicate that the EMM group has different mean self-report craving scores than the SMM group during the treatment phase. The GEE approach with identical link function will be used to fit this hypothesis.

In addition, the efficacy of the BUP/NX with EMM on the mean craving scores during the follow up period using a similar model will be explored.

- b. Effect of craving on treatment outcome: The effect of craving on outcome will be studied by modeling the probability for substantial improvement as a function of treatment, and a measure representing the course of craving during treatment, and their interaction. As measures of craving during treatment, the average craving over the 12 weeks of treatment and the average craving in the last month of treatment or the patient's craving slope from model (1) above will be considered. A significant interaction effect between treatment and the measure of craving would indicate that the level of craving during the treatment period has a different effect on abstinence depending on the treatment. For instance, EMM might be equivalent to SMM among patients without craving, but might be more effective than SMM among patients with a severe course of craving. If the interaction term is not significant, a model with main effects (treatment and course of craving) will be considered and the estimated treatment effect from this model will be compared with the treatment effect estimated from model (1). If the latter is larger (in magnitude) than the former, this would indicate that the course of craving mediates treatment effect and is at least a partial mediator. If the treatment effect from the model with main effect and treatment and course of craving is not significant, this would indicate that craving is a complete mediator of treatment effect.

In addition, the association between the weekly craving and the weekly probability for negative urine will be studied. Appropriate logistic regression models with GEE method of estimation will be used to account for the correlation between the repeated weekly measures and the correlations between patients from the same site.

6. Withdrawal symptoms: the effect of the withdrawal symptoms at baseline in Phase 1 on the outcome of the treatment will be studied. In addition, the signs and symptoms of withdrawal change at the end of the taper period, and at 4- and 8-week followups, will be studied.
7. The relationship between the treatment at Phase 1 and the outcome in Phase 2: the EMM or SMM assignment in Phase 1 is not expected to affect outcome in Phase 2. However, that eventuality will be formally tested. For example, in an exploratory analysis of primary hypothesis 2.1 the following model will be fit:

(1)

$$(2) \text{logit}(Y_{it}) = \beta_0 + \beta_1 txt_{ij} + \beta_2 t I_{ij}^s + \beta_{12} I_{ij}^s txt_{ij} ,$$

where I_{ij}^S is an indicator variable, $I_{ij}^S = 1$ if the subject is in EMM at Phase 1 and $I_{ij}^S = 0$ if the subject is in SMM group at Phase 1. A significant interaction term β_{12} would indicate that the relative efficacy of EMM in Phase 2 depends on the treatment assignment in Phase 1. If β_{12} is not significantly different from 0, the data will be refit with a model without interaction term. GEE approach will be used to fit this model. Similar exploratory analysis will be performed for the secondary hypotheses.

8. Effect of time to failure and pattern of drug use in Phase 1 on the treatment outcome in Phase 2.
9. Age, gender and ethnic differences: the relationship of gender, ethnicity, and age to outcome will be explored.

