2.3.2 Rationale for Pain Assessment and Intervention

The purposes of the pain assessments are:

- To determine the prevalence and characteristics of chronic pain among individuals presenting for treatment of prescription opioid dependence.
- To determine the impact of chronic pain on the outcome of prescription opioid dependence treatment.
- To assess an interaction between chronic pain and treatment in the randomized phase of this study.

Because some participants entering the protocol will have received opioids for pain (perhaps currently), it was desired that pain be addressed in the protocol. However, this is not a pain treatment protocol; it is a treatment for opioid dependence. Treatment of pain per se is beyond the scope of this project. Thus, participants with pain will be asked in each medical management visit about their pain. For pain intervention, participants in both SMM and EMM will receive a self-guided pain management manual (Robert Jamison's patient self-help book; see Appendix F), in both phases. For the EMM group, components will be added to the Pantalon et al., EMM manual that address pain as it impacts recovery from substance dependence (e.g., as a potential trigger for substance abuse relapse); pain will be addressed by the counselors as clinically appropriate (see Appendix F), and will focus on the relationship between pain and substance abuse, which will distinguish it from the SMM treatment. In addition, medical clinicians and counselors will be trained in pain issues. Counselors will be trained in particular about ways in which pain may influence recovery from substance dependence. Study medical clinicians may refer participants with pain to their own physician or to a pain program, but will not be treating the participant for pain (other than briefly for withdrawal discomfort) within the context of the study; e.g., with NSAIDS, etc.

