3.2 Secondary Objectives

Secondary objectives will determine:

- Subject characteristics that predict likelihood of successful outcomes. Measures included in these analyses will include a) pain status; b) reason for initial use of opioids; c) sociodemographic characteristics (sex, race, age); d) severity of withdrawal symptoms; e) severity of craving; f) presence of current or past heroin use; g) presence of other substance use disorders; h) presence of other psychiatric disorders; i) level of depression; and j) number of previous treatment experiences.
- The percentage of this subject population that responds successfully (as defined below) to a 4-week initial treatment with BUP/NX, either with or without concomitant drug counseling.
- Among subjects who have been unsuccessful in a four-week BUP/NX treatment with taper, the overall percentage of subjects who experience substantial improvement with a 12-week BUP/NX stabilization treatment.
- Whether the probability of having positive urine screens for opioids decreases faster over the 12 weeks of Phase 2 stabilization treatment in the EMM group than in the SMM group (Hypothesis: yes).
- Whether EMM subjects will be more likely than SMM subjects to have substantial improvement at the end of 24 weeks of Phase 2, following the taper of BUP/NX during weeks 13-16 and eight weeks of follow-up (Hypothesis: yes).
- The role of pain in determining or moderating the response to EMM.
- The prevalence and nature of adverse events and serious adverse events in this population with this treatment regimen.

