11.2 General Analytic Strategy

11.2.1 Significance Testing

All hypotheses will be tested by two-sided tests with level of significance $\alpha=0.05$. All exploratory analyses will be reported as such and will be thoroughly described in any publication. In particular, the modeling strategy for identification of predictors of outcome (such as inclusion of multiple covariates and interactions) will be explained in detail to allow adequate assessment of the strength of inferences based on data-driven statistical models.

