11.4.3.2 Sample size

A total of 324 subjects will be randomized in Phase 2. Participants in Phase 2 are Phase 1 treatment failures. About 50% of patients enrolled in Phase 1 are expected to be eligible, willing, and to actually enroll in Phase 2. The treatment dropout rate in Phase 2 is expected to be lower than that in Phase 1, since participants in Phase 2 have had experience with the study and have agreed to continue, and because dropout from a stabilization dose of BUP/NX is typically lower than that from a tapering dose. In Phase 2 a rate of about 5% treatment dropout per month is expected, resulting in 15% treatment dropout during the three months of treatment and total of 30% treatment dropout for the entire study (10% treatment dropout per month is expected in Phase 1, or about 30% during the three months of Phase 1).

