	0.40	0.55	0.15	1.36
	0.45	0.60	0.15	1.32
	0.50	0.64	0.14	1.29
1.90	0.20	0.32	0.12	1.61
	0.25	0.39	0.14	1.55
	0.30	0.45	0.15	1.50
	0.35	0.51	0.16	1.44
	0.40	0.56	0.16	1.40
	0.45	0.61	0.16	1.35
	0.50	0.66	0.16	1.31
2.00	0.20	0.33	0.13	1.67
	0.25	0.40	0.15	1.60
	0.30	0.46	0.16	1.54
	0.35	0.52	0.17	1.48
	0.40	0.57	0.17	1.43
	0.45	0.62	0.17	1.38
	0.50	0.67	0.17	1.33

Figure 11.2, page 18 shows how the P_{SMM} , odds ratio, total sample size, and correlation within site (ρ) affect the power. Here, the following assumptions were conservatively made:

- The substantial improvement rate in the SMM group is between 30% and 50%.
- The correlation for each pair of responses (substantial improvement) from the same site is about 0.1.
- Between 20 and 30 patients are recruited from each site.

Figure 11.2 Odds Ratios

Top left: Power vs. the correlation for each pair of the substantial improvement rate from the same site (ρ) given site # = 12, sample size per site = 27, $P_{SMM} = 0.30$ and odds ratio = 1.8, 1.9 and 2.0.

Top right: Power vs. P_{SMM} given site # = 12, sample size per site (Phase 2) = 27, $\rho = 0.1$ and odds ratio = 1.8, 1.9 and 2.0.

Bottom left: Total sample size vs. Power given site # = 12, $P_{SMM} = 0.30$, $\rho = 0.1$, and odds ratio = 1.8, 1.9 and 2.0.

This figure conveys at least 80% power to detect an odds ratio of 1.9 between EMM and SMM group or to detect that the difference in substantial improvement rate between two groups is greater than 16% with $324 = 12 \times 27$ total patients enrolled in Phase 2. If the conservative assumption is made that about 50% subjects enrolled in Phase 1 will actually enroll in Phase 2, then the required sample size in Phase 2 is equivalent to a total sample size 648 in Phase 1.

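### Section 11.4.5 item 1a reads a non-significant pain-by-treatment interaction as proof that EMM efficacy does not depend on chronic pain, though with 324 patients the test would usually miss such dependence

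*Protocol*

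**What the plan says.** Item 1a of Section 11.4.5 first models substantial improvement at three and six months on treatment, pain status and their interaction. It then branches on the interaction test. The lead-in to the second branch is "If the relative efficacy does not depend on baseline chronic pain (lack of significant interaction effect"), and the rule is repeated at the end of the item: "If the interaction effect is not statistically significant at level $\alpha=0.05$, a model with main effects of pain and treatment will be fit". The effect of pain is then estimated from that reduced model. Item 7 uses a similar sequence for the Phase 1 arm: if the interaction is not significant, "the data will be refit with a model without interaction term".

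Moderation by pain is a stated aim. Section 3.2 lists "The role of pain in determining or moderating the response to EMM" among the secondary objectives, and Section 2.3.2 gives as one of three purposes of the pain assessments "To assess an interaction between chronic pain and treatment in the randomized phase of this study".

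The sample size is justified for the overall EMM effect only. Section 11.4.3.2 states "A total of 324 subjects will be randomized in Phase 2", and Section 11.5.3 says of its power figure: "This figure conveys at least 80% power to detect an odds ratio of 1.9 between EMM and SMM group". Section 11.5 gives no power for any interaction.

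**The concern.** The parenthesis in item 1a turns a failure to reject into a finding of no dependence. That is safe only if the test would probably have rejected when efficacy really did differ between pain groups. A trial sized for a main effect has far less power for an interaction of the same size, so a non-significant result is likely whether or not pain matters.

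What is at stake is the answer to a listed secondary objective. EMM could work in one pain group only, and an analyst following item 1a would still probably move on to a model that imposes one EMM odds ratio on both groups.

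**Working it through.** **Inputs from the protocol**
- N = 324, as 12 sites of 27 (Sections 11.4.3.2 and 11.5.3), so 162 per arm at 1:1.
- Two-sided level 0.05 (Section 11.2.1, and item 1a itself).
- Design odds ratio 1.9, SMM rate 0.30-0.50, within-site correlation about 0.1 (Section 11.5.3).

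**Assumptions**
- The protocol gives no chronic pain prevalence for Phase 2, so 20-80% is used.
- SMM rates are equal in the two pain groups.
- Arms are balanced within site and pain group. A within-site correlation ρ then multiplies the variance by (1 − ρ); both ρ = 0 and ρ = 0.1 are shown.

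**Step 1: the protocol's own power figure.** With SMM rate 0.30 and odds ratio 1.9, the EMM rate is 0.57/1.27 = 0.4488, a difference of 0.1488. The pooled rate is 0.3744.
- SE under the null = √(2 × 0.3744 × 0.6256/162) = 0.0538.
- SE under the alternative = √((0.30 × 0.70 + 0.4488 × 0.5512)/162) = 0.0531.
- Power = Φ((0.1488 − 1.96 × 0.0538)/0.0531) = Φ(0.817) = 79.3%, or 83.4% with ρ = 0.1.

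Across SMM rates 0.30-0.50 the range is 79.3-81.9% at ρ = 0 and 83.4-85.8% at ρ = 0.1. The stated figure of at least 80% is reproduced.

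**Step 2: the interaction test from the same inputs.** The test is a Wald test of the log ratio of odds ratios, with variance Σ 1/(n·p·(1 − p)) over the four treatment-by-pain cells. Take a 50/50 pain split (81 per cell), SMM rate 0.30, and odds ratios 1.9 and 1.0. Three cells have rate 0.30 and one has 0.4488.
- Variance = 3/(81 × 0.21) + 1/(81 × 0.4488 × 0.5512) = 0.1764 + 0.0499 = 0.2263, so SE = 0.476.
- z = ln(1.9)/0.476 = 0.642/0.476 = 1.35.
- Power = Φ(1.35 − 1.96) + Φ(−1.35 − 1.96) ≈ 27%.

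Miss rates over SMM rates 0.30-0.50 and ρ of 0 or 0.1:

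| Chronic pain prevalence (assumed) | Miss rate, OR 1.9 vs 1.0 |
|---|---|
| 20% | 77-81% |
| 30% | 72-77% |
| 40% | 69-74% |
| 50% | 68-73% |
| 80% | 78-81% |

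Power is therefore about 19-32%. A small GEE simulation (300 runs per setting, SMM rate 0.30, ρ about 0.1, prevalence 30-50%) gave 25-30%, consistent with this.

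**Step 3: what the trial could detect.** For 80% power against 1.9 versus 1.0 at a 50/50 split and ρ = 0.1, about 1,130-1,260 patients would be needed. With 324 patients, SMM rate 0.30 and ρ = 0, the ratio of odds ratios detectable with 80% power is about 3.8 at a 50/50 split and 4.4 at 30/70.

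**Step 4: a larger contrast.** With odds ratios 3.6 and 1.0, simulation of 4,000 trials per setting gave miss rates of 39%, 22% and 20% at prevalences of 20%, 40% and 50%. The formula in Step 2 gives power of 77-79% at 50/50 with ρ = 0.

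**Step 5: precision at an apparent null.** With all four cells of 81 at rate 0.30, SE = √(4/(81 × 0.21)) = 0.485. An observed ratio of exactly 1 would have a 95% interval of about 0.39 to 2.59, which still contains 1.9.

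**The case against.** The strongest reply is that the clause chooses a model and does not dictate a conclusion. Its next step estimates the effect of pain, not of EMM, and the item's explicit interpretive sentence runs only one way, from a significant interaction to dependence. Section 11.4.5 ranks its own evidence below that for the primary and secondary objectives, and Section 11.2.1 requires exploratory work to be reported as such with the modelling explained. Sizing a trial for its main effect is normal practice.

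Much of this stands, and it limits the point. Several stronger readings might be inferred that the protocol does not support:
- **That the report will say EMM works equally with and without pain.** No section says so; item 1a supplies the equivalence that would invite it.
- **That no pain-specific EMM effect is estimated.** The interaction model is fitted first and contains those effects. The protocol does not require them to be reported, but nothing bars it.
- **That item 7 makes the same claim for the Phase 1 arm.** It only drops the term and never says that efficacy is independent of that arm.
- **That 70-80% is the miss rate for any concentration of the effect in one group.** At a 50/50 split and SMM rate 0.30, odds ratios 1.9 and 1.0 average to an EMM rate of 0.374 and an overall odds ratio of about 1.4, below the design value. If a mean log odds ratio of ln 1.9 lies wholly in one half (1.9² = 3.61 versus 1.0), the miss rate is only about 20%.

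The reply does not rescue the wording. The parenthesis states the equivalence outright, and the exploratory label sits beside a secondary objective that asks this very question.

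**Conclusion.** The point holds for item 1a. Non-significance at 0.05 is written as absence of dependence on chronic pain, and the test is too weak to bear that meaning. It would miss complete loss of the design effect in one pain group about 68-81% of the time, and a contrast of 3.6 versus 1.0 about 20-39% of the time. Both ranges rest on assumed chronic pain prevalences (20-80% for the first, 20-50% for the second). The first also uses SMM rates of 0.30-0.50 and equal SMM rates in the two pain groups.

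The consequence is confined to conclusions about moderation. A reader might infer that the main Phase 2 result is weakened; it is not, because Hypothesis 2.1 is tested by an unadjusted comparison that does not pass through item 1a. The change should be made because it bears on a listed secondary objective and costs little.

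**What to change.** In item 1a, replace the statement that efficacy does not depend on chronic pain with one that no significant interaction is detected. Whatever the p-value, report the ratio of odds ratios with its 95% confidence interval and the EMM versus SMM odds ratio with its 95% interval in each pain group. Add that a non-significant result is not evidence of equal efficacy. For consistency the same estimates can be given by Phase 1 arm in item 7, although no claim there needs to be withdrawn.

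An equivalence range such as 0.5 to 2 should not be added. In the best case (four cells of 81, all rates 0.50) the SE is √(4/(81 × 0.25)) = 0.444, and a 95% interval centred on 1 runs from 0.42 to 2.39. Even with the 0.9 variance factor it is about 0.44 to 2.3, so the range could not be met at this sample size.

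The cost is one change of wording and a few estimates from a model already planned, with no new data. The downside is that the likely report on moderation by pain becomes inconclusive.

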11.2.7 Modeling of Site Effects

The outcomes of subjects from the same site are expected to be correlated. To account for these correlations in the analysis, all tests will be based on Generalized Estimating Equations (GEE) models [Diggle, PJ, Liang K-Y, and Zeger, SL (1994) Analysis of Longitudinal Data, Oxford University Press, Oxford]. GEE approach allows modeling of correlated data that is not necessarily normal, such as the primary outcomes for both Phase 1 and Phase 2. This method is generally robust with respect to misspecification of the correlation structure of the outcome in the sense that it produces unbiased estimates of the parameters in the model for the mean.

The goal of this study is to estimate an overall effect of EMM vs. SMM, rather than to study efficacy in individual sites. There is no evidence that the relative efficacy will differ between sites or that overall efficacy of EMM and SMM will be different in different sites, either for Phase 1 or for Phase 2 study. Therefore, main effects for sites and interaction between sites and treatment will be investigated only as an exploratory analysis.

The GEE approach also allows specification of more than one clustering factor. In this study, in addition to site, repeated measurements over time would constitute another clustering factor. GEE will be used to account for the correlation due to repeated measurements over time and the correlation due to correlation within site.

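### Exploratory item 5b takes a patient's craving slope from a marginal GEE that has none, so the slope version of that analysis (one of three options) says nothing about craving

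*Protocol*

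**What the plan says.** Protocol section 11.4.5 lists exploratory analyses for Phase 2. Item 5 concerns craving.

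- **Item 5a, effect of treatment on craving.** The displayed mean is "E(Y_{ijt}) = \beta_0 + \beta_1 txt_{ij} + \beta_2 t + \beta_{12} t^* txt_{ij} + \beta_{2t} I_{ij}^s", followed by one more term, the product of Phase 1 arm and treatment. The response "is mean craving scores, measured by VAS, of j^{th} patient in the i^{th} site at time t", with t running from 1 to 12. On estimation: "The GEE approach with identical link function will be used to fit this hypothesis".
- **Item 5b, effect of craving on outcome.** The probability of substantial improvement is modelled "as a function of treatment, and a measure representing the course of craving during treatment, and their interaction". Two of the three candidate measures are means of the weekly scores: "the average craving over the 12 weeks of treatment and the average craving in the last month of treatment". The third, offered as an alternative to these, is a rate of change for each person: "craving slope from model (1) above will be considered". If the interaction is not significant, a model with treatment and craving as main effects follows. A smaller treatment effect in that model is to be read as partial mediation by craving, and a non-significant one as complete mediation.
- **Item 7** defines I^s as the Phase 1 arm (1 for EMM, 0 for SMM).
- **Section 11.2.7** sets the general rule: "all tests will be based on Generalized Estimating Equations (GEE) models". Section 11.2.4 names PROC GENMOD for the quantitative outcomes. No model displayed in section 11 contains a random effect or any other patient-specific term.

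**The concern.** A GEE of this kind estimates one mean trajectory for each covariate pattern. Two patients with the same assignments get the same fitted slope, however different their own craving scores were. Item 5b needs the reverse: a measure that varies between patients within an arm, so that its association with outcome can be separated from that of treatment.

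At stake are the conclusions that item 5b attaches to the fit. It would declare craving a moderator, a partial mediator or a complete mediator from coefficients that either cannot be estimated or describe something other than craving.

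**Working it through.** The protocol gives no figure for this analysis, so there is none to reproduce. The check is whether the item 5b designs are identifiable.

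**Inputs.** The item 5a mean model and its GEE fit; the item 5b outcome model; n = 324 in Phase 2 (section 11.4.3.2), as 12 sites × 27 (section 11.5.3). Write txt for the Phase 2 arm (0 or 1), I for the Phase 1 arm (0 or 1) and m for the craving measure. The two designs are [1, txt, m] and [1, txt, m, txt·m].

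**Reading A: the Phase 1-arm terms do not involve time (as printed).** The coefficient of t gives

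- m = β2 + β12·txt, that is β2 in SMM and β2 + β12 in EMM.
- m is therefore β2 times the intercept column plus β12 times the treatment column: rank 2 of 3.
- Since txt² = txt, txt·m = (β2 + β12)·txt, which adds nothing: rank 2 of 4.

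If item 5a falls back to its model without the interaction, m = β2 for everyone. It is then collinear with the intercept, and the ranks are again 2 of 3 and 2 of 4.

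**Reading B: the Phase 1-arm term multiplies time, with coefficient γ.**

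- m = β2 + β12·txt + γ·I, which takes four values, one per combination of assignments.
- Provided γ is not zero, [1, txt, m] spans the same space as [1, txt, I]: rank 3 of 3.
- txt·m = (β2 + β12)·txt + γ·txt·I, so [1, txt, m, txt·m] spans the same space as [1, txt, I, txt·I]: rank 4 of 4.

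This model can be fitted, but it is the Phase 1-by-Phase 2 assignment model that item 7 describes, in other coordinates. To see what the mediation step would compare, let the main-effects fit be c0 + c1·txt + c2·m, and let the same fit in terms of I have coefficients d_txt and d_I. Substituting m gives d_txt = c1 + c2·β12 and d_I = c2·γ, hence

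- c2 = d_I/γ
- c1 = d_txt − (β12/γ)·d_I

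The apparent craving effect is the Phase 1-arm effect rescaled. The craving-adjusted treatment effect is shifted by a multiple of that same Phase 1-arm effect. No patient's craving in relation to that patient's outcome enters either quantity.

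**Numerical check.** For 324 simulated patients (162 per arm assumed, with true slopes differing between patients), the item 5a model was fitted by GEE with identity link and each measure was put into the item 5b designs. The craving scores are invented, but the ranks do not depend on their particular values.

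| Measure | Distinct values | Main effects | With interaction |
|---|---|---|---|
| Item 5a slope, reading A | 2 | 2 of 3 | 2 of 4 |
| Item 5a slope, reading B | 4 | 3 of 3 | 4 of 4 |
| 12-week average | 324 | 3 of 3 | 4 of 4 |
| Last-month average | 324 | 3 of 3 | 4 of 4 |
| Per-patient least-squares slope | 324 | 3 of 3 | 4 of 4 |

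For reading B, the interaction design stacked beside [1, txt, I, txt·I] still has rank 4, which confirms that the two span the same space. The logistic GEE with interaction converged for both averages and for the per-patient slope.

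**The case against.** **The slope is only one option.** It is joined to two averages by the word or, and is merely to be considered. This stands. A reader might infer that item 5b as a whole cannot be fitted. The protocol does not support that: both averages are computed per patient and give full-rank designs, so the moderation and mediation models can be run without the slope.

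**The formula and the reference are unclear.** The time index sits in a subscript in item 5a, while item 7 prints what looks like the matching term with t as a factor. The symbol β12 is used twice in item 5a. Item 5b also cites model (1) a second time, for the treatment effect on outcome, which must be a different model. Some of this may come from the conversion of the PDF. It follows that the rank deficiency should not be stated unconditionally, because it holds under reading A and not under reading B. The lack of patient-level information does not depend on the reading: every model displayed in section 11 is a fixed-coefficient GEE, so no choice of model (1) supplies a patient's slope.

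**The intention is obvious and the detail belongs in the SAP.** The intention is indeed clear. But the protocol does not leave the source of the slope open; it names a model that cannot provide it.

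**The fault would show at the first fit.** Under reading A probably so, though if software silently drops an aliased column, the choice of column decides what is reported as the treatment effect. Under reading B the fit runs without warning.

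**The analysis is exploratory.** This stands and limits the impact. Section 11.4.5 ranks such evidence below that from the primary and secondary objectives, and section 11.2.1 requires exploratory modelling to be labelled and explained.

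**Conclusion.** The phrase is wrong as written, with low impact. The model cited by item 5b cannot yield a patient's craving slope. Under the printed form the slope version is singular (rank 2 of 3 and 2 of 4). Under the alternative form it can be fitted but only re-expresses the two treatment assignments. In neither case can it support a statement that craving moderates or mediates the effect of EMM.

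This rests on two things visible in the protocol: item 5a has fixed coefficients only and is fitted by GEE, and no displayed model in section 11 has a patient-level term. It does not rest on the simulated scores. The choice between readings A and B is the only assumption that matters, and it affects how the analysis fails, not whether it does.

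The 12-week and last-month averages are untouched. No primary or secondary hypothesis, significance level, power figure or sample size depends on the slope. A reader might also infer that any craving slope must stop at Week 8, before the third-month outcome window. That is a separate question of temporal ordering; it has no bearing on the collinearity and is not needed here.

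**What to change.** In section 11.4.5, item 5b, replace the reference to the slope from model (1) with one of the following:

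- the least-squares slope of each patient's weekly craving VAS on week over the 12 weeks of treatment, with a rule for patients who have fewer than two scores; or
- the predicted slope for each patient from a linear mixed model of weekly craving VAS with random intercept and random slope.

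Alternatively, drop the slope and keep the two averages. It would also help to state in item 5a whether the Phase 1-arm term multiplies time, and to give each model its own number.

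The cost is one phrase and, if the slope is kept, one routine additional computation. Craving is already scheduled weekly through Phase 2 treatment (section 10.2.3.4 and Table 4.2), so no new data are needed.
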